Comparisons of treatment responses of early syphilis to 1.0 g single-dose ceftriaxone plus doxycycline versus 2.4 MU single-dose benzathine penicillin G plus doxycycline in people living with HIV

Background

While improvement of access to antiretrovirals for HIV treatment and prevention continue and the case numbers of newly diagnosed HIV infection have stabilized or decreased, sexually transmitted infections (STIs) have been increasing worldwide since late 1990s.¹ Concurrent with the increases in established STIs are emerging epidemics of non-classical sexually transmissible pathogens and co-infections with more than one STI. Furthermore, increases in antimicrobial resistance have limited therapeutic options for STIs, particularly *Neisseria gonorrhoeae* and *Mycoplasma genitalium* infections.²

In Taiwan, we had experienced epidemics and outbreaks of non-classical STIs predominantly affecting men who have sex with men (MSM) living with HIV, such as shigellosis since 2015, acute hepatitis A during 2015-2017, and acute hepatitis C since 2017.³⁻⁵ In addition, syphilis and gonorrhea have been increasingly reported as notifiable diseases over the past decade, while the incidence of HIV infection has significantly decreased since 2018. To facilitate early detection and treatment of individuals with STIs, we have established regular screening for chlamydia, gonorrhea, and syphilis in people living with HIV (PLWH) and MSM receiving pre-exposure prophylaxis (PrEP) in our hospital. In our prospective study investigating the prevalence of STIs among at-risk PLWH, the prevalence of *Chlamydia trachomatis* and *N. gonorrhoeae* was 24.7% and 12.1%, respectively. Surprisingly, we found high rates of *C. trachomatis* and/or *N. gonorrhoeae* co-infections in PLWH with recent hepatitis C virus (HCV) infection (50%), HBsAg positivity (44%), and early syphilis (36%).⁶ Although *C. trachomatis* co-infections have been reported in 20-42% of individuals with *N. gonorrhoeae* infections, few studies document the prevalence of *C. trachomatis* and *N. gonorrhoeae* co-infections among patients with syphilis and viral hepatitis. However, a recent sub-study nested in a randomized controlled trial comparing the efficacy of single dose versus 3 weekly doses of benzathine penicillin G (BPG) for early syphilis also showed a high rate of sexually transmitted co-infections (27%) in patients with early syphilis, including *C. trachomatis*, *N. gonorrhoeae*, and non-gonococcal urethritis.⁷ The findings highlight the importance of integrating bacterial STI screening and treatment into management of early syphilis.

Benzathine penicillin G (BPG) (2.4 million units [MU] intramuscularly once) has been the recommended treatment for early syphilis, but is not effective for treating *C. trachomatis* and *N. gonorrhoeae* co-infections.⁸ The recurrence of BPG shortages has also created an urgent need to identify other alternative treatment that is as effective as BPG for treating early syphilis. Ceftriaxone and doxycycline have been the alternative treatments for

early syphilis; in addition, ceftriaxone (500 mg intramuscularly once) is effective for treating *N. gonorrhoeae* infection, and doxycycline (100 mg orally twice daily for 7 days) effective for treating *C. trachomatis* infection.⁸ However, the current suggested dose of ceftriaxone for early syphilis (1 g intramuscularly or intravenously once daily for 10-14 days) is inconvenient as an outpatient treatment option. Ceftriaxone is long-acting, with treponemacidal levels remaining at 24 hours following injection. According to a small clinical trial, single-dose ceftriaxone achieved a serological response similar to that of BPG.⁹ Considering the high rate of sexually transmitted co-infections, combination therapy of single-dose ceftriaxone plus 7-day doxycycline for early syphilis may provide convenience and benefit to treatment of *N. gonorrhoeae* and *C. trachomatis* co-infections at a single clinic encounter. In the present study, we aim to compare the efficacy of ceftriaxone plus doxycycline versus BPG plus doxycycline as the treatment for early syphilis among PLWH.

Methods

1. Study design: randomized controlled, open-label, non-inferiority study

2. Study site: infectious diseases clinics at the National Taiwan University Hospital (NTUH)

3. Study duration: 2022-2025

4. Enrolled criteria:

(1) PLWH aged 20 years or more

(2) PLWH with early syphilis (i.e. primary, secondary, or early latent syphilis), confirmed by a positive rapid plasma reagin (RPR) titer with a reactive *Treponema pallidum* particle agglutination (TPPA) assay.

(3) PLWH has provided informed consent

*A participant with repeated syphilis can be repeated enrolled after signing an informed consent if the previous episode of early syphilis was successfully treated with achieving at least a 4-fold decrease in RPR titers and 48-week follow-up is completed.

5. Exclusion criteria:

(1) PLWH with RPR titers of less than 4

(2) Exposure to antibiotics with activity against *T. pallidum*, such as penicillins, third-generation cepheems, doxycycline, or macrolides, within the preceding 4 weeks

(3) A known or suspected infection other than syphilis requiring additional treatment with an antimicrobial active against *T. pallidum*

(4) A history of intolerance to penicillin, ceftriaxone, or doxycycline

(5) Pregnancy

6. Study procedures: participants will be randomized in a 1:1 ratio to receive ceftriaxone plus doxycycline or BPG plus doxycycline. Randomization will be stratified by the stage of syphilis and RPR titer at baseline.

Arm 1: single-dose ceftriaxone (1g intramuscularly once) plus doxycycline (100 mg orally twice daily for 7 days)

Arm 2: single-dose BPG (2.4 MU intramuscularly once) plus doxycycline (100 mg orally twice daily for 7 days)

7. Baseline and follow-up testing:

Proof of concept phase: (enrolled 50 participants in each group)

- (1) Questionnaire for socio-epidemiologic characteristics and sexual history at baseline and weeks 24, 48
- (2) Serum RPR at baseline and weeks 4, 12, 24, 36, and 48
- (3) *T. pallidum* PCR (TP-PCR) for self-collected specimens from oral rinse, urethral, and rectal sites at baseline, weeks 1, 2, 3, 4, 12, 24, 36, and 48 (specimens collected in weeks 1, 2, and 3 were optional)
- (4) Bacterial STIs (*C. trachomatis*, *N. gonorrhoeae*, *Mycoplasma genitalium*, *M. hominis*, *Ureaplasma urealyticum*, *U. parvum*) for self-collected specimens from oral rinse, urethral, and rectal sites at baseline and week 4
- (5) Resistance-associated mutations (RAM) of *T. pallidum* and other sexually transmitted bacteria at baseline

	Baseline	Wk1 (±2 days)	Wk2 (±2 days)	Wk3 (±2 days)	Wk4 (±2 days)	Wk12 (±2 weeks)	Wk24 (±2 weeks)	Wk36 (±2 weeks)	Wk48 (±2 weeks)
Questionnaire	v						v		v
Doxycycline compliance record		v							
RPR	v				v	v	v	v	v
TP-PCR	v	v	v	v	v	v	v	v	v
		(optional)							
Bacterial STIs	v				v				
RAM	v								

Continuation phase: (enrolled 100 participants in each group)

- (1) Questionnaire for socio-epidemiologic characteristics and sexual history at baseline and

weeks 24, 48

(2) Serum RPR at baseline and weeks 4, 12, 24, 36, and 48

(3) *T. pallidum* PCR (TP-PCR) for self-collected specimens from oral rinse, urethral, and rectal sites at baseline, weeks 4, 12, 24, 36, and 48

(4) Bacterial STIs (*C. trachomatis*, *N. gonorrhoeae*, *M. genitalium*, *M. hominis*, *U. urealyticum*, *U. parvum*) for self-collected specimens from oral rinse, urethral, and rectal sites at baseline and week 4

(5) Resistance-associated mutations (RAM) of *T. pallidum* and other sexually transmitted bacteria at baseline

	Baseline	Wk1 (±2 days)	Wk2 (±2 days)	Wk3 (±2 days)	Wk4 (±2 days)	Wk12 (±2 weeks)	Wk24 (±2 weeks)	Wk36 (±2 weeks)	Wk48 (±2 weeks)
Questionnaire	v						v		v
Doxycycline compliance record		v							
RPR	v				v	v	v	v	v
TP-PCR	v				v	v	v	v	v
Bacterial STIs	v				v				
RAM	v								

8. Duration of study: Participants will be followed for at least 48 weeks.

9. Primary outcome:

Serologic response at month 6 (defined as either a 4-fold or greater decline in RPR titer compared to baseline or being RPR-nonreactive)

10. Secondary outcomes:

(1) Microbiologic response of syphilis (defined as *T. pallidum* PCR Ct value >38) at week 4

(2) Microbiologic response of bacterial STIs (defined as negative PCR results) at week 4

(3) Serologic response at months 3 and 12

(4) Safety of study treatment recorded by using a diary (all adverse events will be coded and graded according to Common Terminology Criteria for Adverse Events [CTCAE] v4.0.)

(5) Adherence evaluation (the noting of tablet intake in the diary for the 7 days of the treatment period)

11. Futility stopping rules:

(1) In the proof-of-concept phase, microbiologic and/or serologic response of syphilis

(microbiologic response was defined as *T. pallidum* PCR Ct value >38, and serologic response was defined as at least a 4-fold decrease in RPR titers) at week 4 will be compared between study groups. The non-inferiority margin of 10% will be used as the futility stopping rule in the proof-of-concept phase.

(2) Participants with treatment failure at week 24 will receive standard-of-care treatment (BPG 2.4 MU intramuscularly once). Treatment failure is defined as at least a 4-fold increase in RPR titers compared with the baseline RPR or at least a 4-fold increase in RPR titers after achieving serologic response during follow-up. Participants who received additional treatment with an antimicrobial active against *T. pallidum* (i.e. penicillins, third-generation cepheems, doxycycline, or macrolides) will also be excluded from the study.

(3) The continuation phase will be conducted only if microbiologic response of syphilis is non-inferior in the ceftriaxone plus doxycycline group compared with the BPG plus doxycycline group.

Laboratory investigations

1. *T. pallidum* PCR:

T. pallidum PCR will be performed on specimens from oral rinse, urine, rectal sites, blood, and lesions of syphilis. Treponemal DNA will be extracted with the QIAamp DNA mini Kit. The diagnostic PCR assay will be used to amplify the 47 kDa protein membrane gene (*tpp47*).

2. Bacterial STIs screening:

The screening for bacterial STIs, including *C. trachomatis*, *N. gonorrhoeae*, *Trichomonas vaginalis*, *Mycoplasma* spp., and *Ureaplasma* spp.) will be performed on self-collected specimens from oral rinse, urethral, and rectal sites with the use of multiplex real-time PCR assay on an automated system.

3. Resistance-associated mutation of *T. pallidum*

Single-nucleotide polymorphisms (SNPs) will be determined at positions A2058G or A2059G of the 23S rRNA gene, as well as positions 965–967, 926–928, 939 and 1058 of the 16S rRNA gene.

Statistical analysis

According to the previous randomized controlled, open-label study conducted by Cao Y et al, the serological response of early syphilis at 6 months of follow up was observed in 90.2% in ceftriaxone group and 78.0% in BPG group.¹⁰ Therefore, at least 150 participants would be

required for each treatment group to detect a between-group difference, with a two-sided significance level of 5% and a power of 80%. The intention-to-treat population is defined as all patients who undergo randomization except for those who do not provide consent for the use of their data. The analyses will be performed through the FDA snapshot algorithm in the ITT population, which categorizes outcomes into success, failure, and no data in window. The Categorical variables will be compared by Fisher's exact test or Chi-square test. Non-categorical variables will be compared by Mann-Whitney U test. Factors with P value ≤ 0.2 , or with biological significance will be included for multivariate analysis. Logistic regression analysis will be used to determine the factors associated with serologic responses after treatment. All comparisons will be two-tailed and a P value <0.05 is considered significant. All statistical analyses were performed with the use of STATA software version 17.0 (Stata Corporation, College Station, TX).

References

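### Randomisation is stratified by syphilis stage and baseline RPR titre, but the only between-group test named for the binary primary outcome ignores the strata: a modest, cheaply recovered loss of efficiency, not a validity error

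*Combined protocol and SAP*

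**What the plan says.** - **Design.** Methods item 1 describes a "randomized controlled, open-label, non-inferiority study". Item 6 says "participants will be randomized in a 1:1 ratio" and then "Randomization will be stratified by the stage of syphilis and RPR titer at baseline". The RPR cut-points and the number of strata are not given. Item 4 lists three stages of early syphilis.
- **Primary outcome.** Methods item 9 makes it binary: "Serologic response at month 6 (defined as either a 4-fold or greater decline in RPR titer compared to baseline or being RPR-nonreactive".
- **Analysis.** The Statistical analysis section compares categorical variables by Fisher's "exact test or Chi-square test". It names no stratified test, no stratified risk difference and no model that must contain the stratification factors.
- **Regression.** A logistic model is planned to find factors associated with serologic response. Factors enter if P is at most 0.2, "or with biological significance will be included for multivariate analysis".
- **Margin.** A 10% margin appears only in Methods item 11, as the futility rule of the proof-of-concept phase.

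**The concern.** Stratified randomisation balances the arms on stage and titre. If those factors predict response, the balance removes between-stratum variation from the true sampling error of the treatment difference. An unstratified test still counts that variation in its variance, so it understates the precision achieved. At stake is some power in a trial of about 150 per arm. The plan gives no reason for choosing the two factors. Baseline RPR does, however, enter the definition of the primary outcome, so a link with response is plausible.

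**Working it through.** **1. The plan's own figure.** Inputs from the Statistical analysis section: 90.2% vs 78.0%, two-sided 5%, 80% power, 150 per group. Exact enumeration for Fisher's test gives 153 per group for 80% power, and 79.2% power at 150. The pooled normal formula gives 140 per group, and 82.7% power at 150. So 150 agrees with Fisher's test to within 3 participants, and the sample size takes no account of strata.

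**2. Variance with and without strata.** Assumed inputs: two strata with weights w = 0.6 and 0.4, response p₁ and p₂, the same in both arms.

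- Overall response: p̄ = Σ w·p
- Variance ratio, stratified to unstratified: R = Σ w·p(1−p) / [p̄(1−p̄)]
- Equivalent extra participants per arm: 150 × (1/R − 1)
- Approximate type I error of the unstratified test: 2 × [1 − Φ(1.96/√R)]

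| p₁ vs p₂ | p̄ | Σ w·p(1−p) | p̄(1−p̄) | R | Extra per arm | Type I error, unstratified |
|---|---|---|---|---|---|---|
| equal | – | – | – | 1.000 | 0 | 5.0% |
| 90% vs 82% | 0.868 | 0.1130 | 0.1146 | 0.987 | 2.0 | 4.8% |
| 90% vs 75% | 0.840 | 0.1290 | 0.1344 | 0.960 | 6.3 | 4.5% |
| 90% vs 65% | 0.800 | 0.1450 | 0.1600 | 0.906 | 15.5 | 4.0% |

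**3. Non-inferiority power in the last row.** Assumptions: 80% response overall in both arms, a 10% margin applied to the primary outcome, 150 per arm.

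- Unstratified: SE = √(2 × 0.160/150) = 0.0462; Φ(0.10/0.0462 − 1.96) = Φ(0.205) = 58.1%
- Stratified: SE = √(2 × 0.145/150) = 0.0440; Φ(0.10/0.0440 − 1.96) = Φ(0.314) = 62.3%

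**4. Simulation with six strata.** Assumptions: three stages by two RPR levels, equal in size, exact balance within strata, 150 per arm, no dropout, 40,000 trials per scenario. The odds ratio (OR) applies between the extreme stages and, separately, between the RPR levels. CMH is the Cochran-Mantel-Haenszel test.

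| OR | Superiority power, chi-square / CMH (90.2% vs 78.0%) | Non-inferiority power, unstratified / stratified (both 78%, 10% margin) | Type I error, chi-square / CMH |
|---|---|---|---|
| 1 | 83.4% / 83.4% | 55.5% / 55.1% | 5.0% / 4.9% |
| 2 | 83.7% / 84.4% | 55.9% / 56.8% | 4.6% / 4.9% |
| 4 | 84.5% / 86.8% | 56.0% / 60.3% | 3.7% / 5.0% |
| 6 | 85.2% / 88.6% | 56.0% / 63.1% | 3.2% / 5.1% |

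When the true difference equals the 10% margin (68% vs 78%), the unstratified interval falsely declares non-inferiority in 2.5%, 2.4%, 1.7% and 1.4% of trials at OR 1, 2, 4 and 6. The stratified interval stays at 2.4% to 2.6%. The unstratified analysis therefore errs on the cautious side.

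**The case against.** The strongest reply is that nothing here is invalid and that the gain may be trivial. The documents contain no response rates by stage or titre, and the larger gains need strong effects: 90% vs 65% is an odds ratio of about 4.9, and 90% vs 75% is 3. At an odds ratio near 2 the gain is about 2 participants per arm, or roughly one point of power. Six or more strata could also be sparse. Six equal strata would hold 25 participants per arm each, and at 90.2% response only about 2.5 of them (25 × 0.098) would be non-responders. All of this stands. It limits the size of the point but does not remove it, because stratifying costs at most a fraction of a point of power when the factors are not prognostic (55.5% vs 55.1%).

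A reader might infer four stronger things that the documents do not support:

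- **That P-value screening compromises the treatment estimate.** Entry is not by P value alone; biological significance is a second route, by which stage, titre and arm could all enter. The model is described as a search for factors associated with response, not as the treatment comparison.
- **That the plan's primary confidence interval is too wide.** The plan names no such interval.
- **That the trial is already short of non-inferiority power.** This depends on assuming equal response in the two arms. At the plan's own rates, with a 10% margin and 150 per arm, power exceeds 99%.
- **That repeat enrolment undermines the tests.** Methods item 4 does allow it: "A participant with repeated syphilis can be repeated enrolled after signing an informed consent if the previous episode of early syphilis was successfully treated". It also requires 48 weeks of completed follow-up. In a simulation with assumed repeat rates of 15% to 25% and assumed within-person correlation, type I error was 5.0% to 5.7%. This is too small, and rests too much on assumption, to be a reason for change.

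**Conclusion.** The mismatch between a stratified design and an unstratified test is real. Its consequence is a conservative test and some lost precision, conditional on stage and RPR titre predicting response. Over the assumed scenarios the loss runs from nothing to about 16 participants per arm in the two-stratum calculation. In the six-stratum simulation it reaches about 3.4 points of superiority power (85.2% to 88.6%) and 7.1 points of non-inferiority power (56.0% to 63.1%). The documents do not show where in that range the trial lies. The non-inferiority figures rest further on equal response in both arms and on carrying the 10% proof-of-concept margin over to the primary outcome. The change is worth making because it is nearly free, not because the planned test would mislead.

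**What to change.** - Make the primary treatment comparison a Mantel-Haenszel risk difference with 95% CI (or a stratified Newcombe or Miettinen-Nurminen interval), stratified by stage and by the RPR categories used at randomisation.
- State those RPR categories in the plan, with a rule, fixed before the data are seen, for collapsing sparse strata.
- If the logistic model is also used to report an adjusted treatment estimate, always include arm, stage and baseline RPR. Keep the rule based on P value or biological significance for the exploratory factor analysis only.

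The cost is a short SAP amendment and a few lines of Stata code, with no new data or participants. The one small downside is the possible need to collapse strata, which the pre-stated rule covers.

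### Microbiologic response is judged on week 4 alone, so participants PCR-negative at baseline count as responders and shrink the difference that gates the continuation phase

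*Combined protocol and SAP*

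**What the plan says.** - **Eligibility** (Methods 4(2)) covers primary, secondary and early latent syphilis, "confirmed by a positive rapid plasma reagin (RPR) titer with a reactive" TPPA. A positive *T. pallidum* PCR is not required.
- **Syphilis outcome** (Methods 10(1)): "Microbiologic response of syphilis (defined as *T. pallidum* PCR Ct value >38) at week 4". Methods 11(1) repeats the same cut-off for the futility comparison. Neither refers to the baseline result, whereas the primary serologic outcome is a change from baseline.
- **Bacterial STI outcome** (Methods 10(2)): "Microbiologic response of bacterial STIs (defined as negative PCR results) at week 4", again with no baseline condition.
- **Gate** (Methods 11(1) and 11(3)): "The non-inferiority margin of 10% will be used as the futility stopping rule in the proof-of-concept phase", and "The continuation phase will be conducted only if microbiologic response of syphilis is non-inferior in the ceftriaxone plus doxycycline group" when set against the BPG group. The gate is read after 50 participants per group.
- **Analysis set** (Statistical analysis): ITT is everyone randomised apart from those who refuse use of their data, and "The analyses will be performed through the FDA snapshot algorithm in the ITT population". No PCR-evaluable or baseline-positive set is defined.
- **Specimens**: Methods 7 schedules *T. pallidum* PCR "for self-collected specimens from oral rinse, urethral, and rectal sites at baseline, weeks 1, 2, 3, 4, 12, 24, 36, and 48" in the proof-of-concept phase. Laboratory investigations 1 says that "PCR will be performed on specimens from oral rinse, urine, rectal sites, blood, and lesions of syphilis".

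**The concern.** A participant without detectable organism at baseline has nothing to clear. If that participant is still negative at week 4, the stated definition scores a response, and it does so equally in both arms. Such participants carry no information on whether the drug cleared the organism, yet they enter both numerators and both denominators and pull the two response rates together.

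In a superiority comparison this costs power. In a non-inferiority comparison it favours passing. Methods 11(3) makes this outcome the condition for enrolling the continuation phase, a further 100 participants per group. The safeguard is therefore weaker than a 10% margin suggests, and both microbiologic secondary outcomes understate any difference in clearance.

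**Working it through.** **Inputs from the plan.** 50 participants per group at the gate; a 10% margin; 36% *C. trachomatis* and/or *N. gonorrhoeae* co-infection among PLWH with early syphilis (Background). The plan has no calculation for the gate to reproduce. Its 150 per group concerns month-6 serology and does not enter here.

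**Assumed, because the plan gives no figure.** f, the share *T. pallidum* PCR-positive at baseline (0.8, 0.5, 1/3), and the clearance rates among those participants. For simplicity f is the same in both arms, baseline-negatives stay negative, and no week-4 result is missing.

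**Step 1: dilution.** With clearance p among baseline-positives, the all-randomised response is f × p + (1 − f). The between-arm difference is therefore f × (difference in p). Example with f = 0.5 and clearance of 90% (BPG) against 75% (ceftriaxone):
- BPG: 0.5 × 0.90 + 0.5 = 0.950
- Ceftriaxone: 0.5 × 0.75 + 0.5 = 0.875
- Difference: −7.5 points, against −15 points among baseline-positives.

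**Step 2: what the margin tolerates.** A 10-point margin on all randomised equals 10/f points among baseline-positives: 10/0.8 = 12.5, 10/0.5 = 20, 10/(1/3) = 30.

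**Step 3: bacterial STIs.** Taking f = 0.36 for *C. trachomatis*/*N. gonorrhoeae*, a 10-point all-randomised difference corresponds to 10/0.36 = 28 points among the infected. The plan gives no early-syphilis figure for the other organisms in the panel. This outcome does not gate.

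**Step 4: chance of passing the gate.** The plan does not say whether the 10% applies to the point estimate or to a confidence bound, so both are shown. The figures come from exact binomial enumeration. PE = observed difference above −10 points; CI = Newcombe 95% lower limit above −10 points. The baseline-positive rows use the expected number, 50 × f per arm.

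| f | Counted per arm | 75% v 90%: PE | 75% v 90%: CI | Equal 90%: PE | Equal 90%: CI |
|---|---|---|---|---|---|
| 0.8 | all 50 | 33% | 1.1% | 95% | 39% |
| 0.8 | 40 positive | 23% | 0.5% | 91% | 26% |
| 0.5 | all 50 | 61% | 5.6% | 98% | 51% |
| 0.5 | 25 positive | 32% | 0.9% | 88% | 19% |
| 1/3 | all 50 | 81% | 14% | 99% | 59% |
| 1/3 | 17 positive | 31% | 0.8% | 81% | 11% |

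The pattern is the same with 95% against 75% clearance and a Wald bound. At f = 0.5 the pass chance is 43% (PE) or 5% (CI) with all 50 counted, and 15% or 0.4% with 25.

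**Step 5: what the subset can bear.** If all 25 per arm clear in both groups, the Newcombe lower limit is −(1 − 25/(25 + 1.96²)) = −(1 − 25/28.84) = −13.3 points, so the CI rule fails. About 35 per arm are needed before complete clearance in both groups passes. For 80% power with 95% clearance in both groups, the usual formula gives (1.96 + 0.84)² × 2 × 0.95 × 0.05 / 0.10² ≈ 75 baseline-positive participants per arm, or about 150 enrolled per arm at f = 0.5.

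**The case against.** **The denominator is inferred.** The ITT sentence is general, follows a sample-size statement about serology, and mentions neither PCR nor the gate. Baseline PCR is scheduled, so an analysis of baseline-positives may have been intended. This stands as a comment on intent. It does not change the reading of the text: ITT is the only set defined and nothing overrides it for these outcomes.

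**Not every baseline-negative participant is a success.** A reader might infer that they succeed automatically, whatever happens. The plan does not support that. Under the snapshot algorithm a missing week-4 result falls under no data in window, and the week-4 window is only ±2 days. A newly positive week-4 result is not a response either. The point holds for those still negative at week 4.

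**The gain is easily overstated.** At f = 0.5 one could set the plan's 5.6% or 61% beside the 0.4% or 21% that apply when all 50 per arm are baseline-positive. That is not an available alternative, because restricting the denominator leaves about 25 per arm. The fair comparison is 5.6% against 0.9% (CI), or 61% against 32% (PE).

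**Restriction can break the gate.** This stands for a confidence-bound rule, as Steps 4 and 5 show. Under a point-estimate rule the cost is milder: 98% falls to 88% at f = 0.5 with equal clearance.

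**The specimen lists differ in scope.** One covers scheduled self-collected samples and the other the sample types the assay is run on. Blood and lesions in the second list do not contradict the first. Only urethral against urine is a wording mismatch. Which sites must clear is unstated, not inconsistent.

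**Conclusion.** The concern holds. Read as written, the plan counts participants who are PCR-negative at baseline and still negative at week 4 as microbiologic responders, and it multiplies any difference in clearance by f. The direction follows from the definitions. The size for *T. pallidum* cannot be known from the documents: the tolerated deficits of 12.5, 20 and 30 points rest on assumed f, and the pass probabilities also rest on assumed clearance. The figure of 0.36 for *C. trachomatis*/*N. gonorrhoeae* rests on the sponsor's earlier cohort applying to this trial.

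Three stronger conclusions are not supported:
- The microbiologic outcomes are not beyond rescue, because baseline PCR is collected and the relevant subset can be identified.
- The primary outcome is not affected. It is serologic, measured at month 6 and defined against baseline.
- It does not follow that the gate should rest on baseline-positives alone. At 50 enrolled per arm that is a trade-off between a diluted comparison and an underpowered one.

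**What to change.** 1. **Secondary outcomes 10(1) and 10(2).** Analyse each in participants PCR-positive at baseline for the organism concerned. Define response as the sampled sites being negative at week 4 (Ct >38 for *T. pallidum*). Give the all-randomised result as supportive.
2. **Gate in 11(1) and 11(3).** Report the baseline-positive comparison beside the all-randomised one. State whether the 10% applies to the point estimate or to a confidence bound, and at what level. State the expected baseline PCR positivity, so that the number of informative participants is known in advance. Do not simply transfer a 95% confidence rule to the subset at the present size.
3. **Wording.** Reconcile urethral in Methods 7 with urine in Laboratory investigations 1.

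The cost is protocol and SAP text; no new sampling is needed, because the baseline specimens are already scheduled. The downside is fewer evaluable participants and wider intervals, about 25 per arm at the gate if half are PCR-positive at baseline.

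### Treatment failure is defined over the whole follow-up but acted on only at week 24, and the same participant can be both a failure and a month-6 responder

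*Combined protocol and SAP*

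**What the plan says.** Methods 11(2) of the combined protocol and SAP attaches one action to one visit: "Participants with treatment failure at week 24 will receive standard-of-care treatment". The definition that follows names no visit. Its first limb reads "Treatment failure is defined as at least a 4-fold increase in RPR titers compared with the baseline RPR"; its second is "at least a 4-fold increase in RPR titers after achieving serologic response during follow-up". The same item ends by stating that anyone given additional antimicrobials active against *T. pallidum*, penicillins among them, "will also be excluded from the study".

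The testing schedule in Methods 7 is the same in both phases: "Serum RPR at baseline and weeks 4, 12, 24, 36, and 48". Methods 8 adds "Participants will be followed for at least 48 weeks".

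Methods 9 sets the primary outcome as serologic response at month 6, "defined as either a 4-fold or greater decline in RPR titer compared to baseline or being RPR-nonreactive". Methods 10(3) lists "Serologic response at months 3 and 12" as a secondary outcome. The Statistical analysis section takes as ITT everyone randomised, apart from those who withhold consent to use of their data. It applies the FDA snapshot, which sorts participants into success, failure or absence of data in the window. Treatment failure as defined in 11(2) is not mentioned there.

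**The concern.** Three passages do not fit together.

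First, the definition in 11(2) can be met at any post-baseline RPR reading, but the text is silent on what follows unless the reading is at week 24.

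Second, the primary outcome looks only at the month-6 titre against baseline. Failure can also be a rise from a lower titre reached in between. The two rules can therefore give opposite answers for one participant, and none is given precedence.

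Third, retreated participants are removed by 11(2) but retained by the ITT definition, with no snapshot category assigned.

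At stake is what a month-6 responder means. The trial is open-label with a non-inferiority aim. If the rule is not fixed beforehand, the classification will be settled by people who know the arm. Counting defined failures as successes, or dropping them, raises the rate of whichever arm has more of them. If that is the ceftriaxone arm, the error favours non-inferiority.

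**Working it through.** The plan gives no figure on this point to reproduce. The check compares the passages and works through the titre rules. The only number taken from the plan for size is 150 per group.

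**1. Visits, actions and outcomes.** Months 3, 6 and 12 are taken as weeks 12, 24 and 48.

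| RPR reading | Failure limbs that can apply | Action stated in 11(2) | Serologic outcome at that reading |
|---|---|---|---|
| Week 4 | Rise over baseline only (no earlier post-baseline titre could show response) | None | Proof-of-concept futility comparison only |
| Week 12 | Both | None | Month 3, secondary |
| Week 24 | Both | Yes | Month 6, primary |
| Week 36 | Both | None | None |
| Week 48 | Both | None | Month 12, secondary |

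Four of the five readings have no stated action.

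**2. Rise over baseline, same visit.** A titre at least 4 times baseline cannot also be at most a quarter of baseline. At weeks 12, 24 and 48 this limb is therefore non-response at that reading, and there is no conflict.

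**3. Rise after response, same visit.** Write baseline as 1:2^b, the titre at response as 1:2^x and the later titre as 1:2^y. Let 1:1 be the lowest reactive titre (x ≥ 0), and measure the rise from the titre at response.
- Response: x ≤ b − 2.
- Failure after response: y ≥ x + 2.
- Still a responder at the later reading: y ≤ b − 2.

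All three hold only if x + 2 ≤ b − 2, so b ≥ x + 4 ≥ 4. Baseline must be at least 1:2^4 = 1:16. The smallest case is 1:16, 1:1, 1:4.

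Example: baseline 1:32, week 12 1:2, week 24 1:8.
- Week 12: 32/2 = 16-fold fall, so response.
- Week 24 against week 12: 8/2 = 4-fold rise, so treatment failure under 11(2).
- Week 24 against baseline: 32/8 = 4-fold fall, so primary-outcome response under Methods 9.

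**4. Early rise over baseline, later response.** Example: baseline 1:4, week 12 1:16, week 24 1:1. At week 12, 16/4 = 4, so failure. At week 24, 4/1 = 4, so response. No rule says whether the earlier failure carries forward. This route needs at least a 16-fold fall between the two readings (4 × 4), so it is more demanding than the one in step 3.

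**5. Size.** One participant whose status changes moves an arm's rate by 1/150 = 0.0067, or 0.67 points.

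For the exclusion wording, take the plan's 78.0% for BPG as an illustration: 0.78 × 150 = 117 responders. Assume k of the 33 non-responders are failures who were retreated.
- Kept in the denominator as failures: 117/150 = 78.0%.
- Dropped, k = 1: 117/149 = 78.5%.
- Dropped, k = 5: 117/145 = 80.7%.

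The values of k are assumptions chosen to show the arithmetic; the documents give no failure rate.

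**The case against.** The strongest reply is the last sentence of 11(2). A reader might infer that a ceftriaxone participant who fails at week 12, receives BPG and then falls to a quarter of baseline would be scored as a ceftriaxone success. As written, that participant leaves the study because BPG is a penicillin, so the documents do not support that inference. This part of the reply stands. It does not settle the snapshot category, because the ITT definition still retains the participant. Nor does it touch the step 3 example, where the week-24 titre is read before any retreatment prompted by it.

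It is also fair to say that silence is not prohibition. A reader might infer that 11(2) imposes a wait of 12 or 20 weeks after a rise at week 12 or week 4. The text does not forbid earlier treatment, and the exclusion sentence anticipates additional treatment at any time. Reading the rule as acting at week 24 on any failure up to then would cover weeks 4 and 12, but still leaves weeks 36 and 48 without a stated action.

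Other strong readings fail too. It is not true that these failures have no endpoint status: a rise over baseline is non-response at months 3, 6 and 12. Uneven handling between centres cannot be argued, since Methods 2 names one hospital. A bias of several points set against the 10% margin is unsupported: no failure rate is given, and that margin is stated only for the week-4 futility rule.

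**Conclusion.** The point holds as a conflict between the plan's own rules, and it should be corrected. The failure definition covers five readings and the stated action covers one. For baselines of 1:16 or higher, one set of titres can be both a defined treatment failure and a primary-outcome success, and an earlier rise over baseline can be replaced by a favourable week-24 titre. Retreated participants are excluded by one section and retained by another, with no category assigned.

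The effect is 0.67 points per reclassified participant in an arm of 150. The total cannot be estimated from the documents. It may be small, and its direction depends on which arm has more such participants.

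This rests on two readings of the text: the rise after response is measured from a post-response titre (measured from baseline, the second limb would add nothing to the first), and 1:1 is the lowest reactive titre. A rise from a nonreactive result was left out because the plan does not say how to count its fold change.

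**What to change.** - **Methods 11(2):** reconcile the failure definition with the visits at which it is acted on. The clinical rule is for the investigators to choose.
- **Methods 9 and Statistical analysis:** state that a participant who meets the failure definition at any visit up to and including week 24 counts as a failure (non-responder) in the month-6 ITT snapshot, whatever the later titre or treatment.
- **Methods 11(2), last sentence:** reword the exclusion so that it does not remove these participants from the ITT denominator.

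The cost is a few sentences in three places, with no new visits or tests. Reported response rates may be slightly lower. Some rises may be reinfections counted as failures, but the protocol's own definition already counts them that way.
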